3. **Slit lamp examination (SLE):** The slit lamp examination must be performed before the instillation of any dilating or anesthetic eye drops or the fluorescein agent.

The subject will be seated at the slit lamp while being examined. Grading of the eyelids, lashes, conjunctiva, cornea, lens, iris and anterior chamber will be done according to the following scales:

Eyelid - Meibomian glands (evaluation of the central ten Meibomian gland openings in the mid-portion of the upper eyelid):

0 = None (none are plugged).

1 = Mild (1 to 2 glands are plugged).

2 = Moderate (3 to 4 glands are plugged).

3 = Severe (All glands are plugged).

Eyelid - Erythema

0 = None (normal).

1 = Mild (redness localized to a small region of the lid(s) margin OR skin).

2 = Moderate (redness of most or all lid margin OR skin).

3 = Severe (redness of most or all lid margin AND skin).

4 = Very severe (marked diffuse redness of both lid margin AND skin).

Eyelid - Oedema

0 = None (normal).

1 = Mild (localized to a small region of the lid).

2 = Moderate (diffuse, most or all lid but not prominent/protruding).

3 = Severe (diffuse, most or all lid AND prominent/protruding).

4 = Very severe (diffuse AND prominent/protruding AND reversion of the lid).

Lashes

0 = Normal

1 = Abnormal (specify)

Conjunctiva - Erythema

0 = None (normal).

1 = Mild (a flush reddish color predominantly confined to the palpebral or bulbar conjunctiva).

2 = Moderate (more prominent red color of the palpebral or bulbar conjunctiva).

3 = Severe (definite redness of palpebral or bulbar conjunctiva).

Conjunctiva - Oedema

0 = None (normal).
1 = Mild (slight localized swelling).
2 = Moderate (moderate/medium localized swelling or mild diffuse swelling).
3 = Severe (severe diffuse swelling).
4 = Very severe (very prominent/protruding diffuse swelling).

Lens

0 = No opacification (normal lens).
1 = Mild lens opacification.
2 = Moderate lens opacification.
3 = Severe lens opacification.
N/A = Subject with artificial lens

Iris

0 = Normal
1 = Abnormal.

Anterior Chamber Inflammation (Slit beam = 0.3 mm wide, 1.0 mm long)

0 = None (no Tyndall effect).
1 = Mild (Tyndall effect barely discernible).
2 = Moderate (Tyndall beam in the anterior chamber is moderately intense).
3 = Severe (Tyndall beam in the anterior chamber is severely intense).

Cornea transparency

0= completely transparent
1= mild opacity
2= moderate opacity (iris details clearly visible)

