8.11.4.6 Slit lamp examination

The scores of slit lamp examination (Eyelid - Meibomian glands, Eyelid - Erythema, Eyelid - Oedema, Lashes, Conjunctiva - Erythema, Conjunctiva - Oedema, Lens, Iris, Anterior Chamber Inflammation, Cornea transparency and Cornea neovascularization) and their changes from day 1 - pre-dose values and day 15±2 - pre-dose values for the study/primary eye and for the non-study/secondary eye will be listed ([Listing 16.2.6.7](#)) and summarised by treatment and time point using descriptive statistics (mean, SD, CV%, minimum, median and maximum) ([Table 14.2.1.7](#)).

The changes from day 1 - pre-dose values at day 15±2 pre-dose will be compared between treatments using a Wilcoxon Rank Sum Test ([Table 14.2.2.7](#)).

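### The Meibomian gland scale assesses ten openings but defines no grade for 5 to 9 plugged, so an eye in that range cannot be scored as the protocol is written

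*Protocol*

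**What the plan says.** Protocol section 6.4.1.1, under the slit lamp examination, makes the listed scales the grading rule: "Grading of the eyelids, lashes, conjunctiva, cornea, lens, iris and anterior chamber will be done according to the following scales". For the Meibomian glands it sets the field of view as "evaluation of the central ten Meibomian gland openings in the mid-portion of the upper eyelid" and gives four grades:

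- The lowest grade, 0, is for an eye with no plugged opening.
- Grade 1 is for an eye with one or two.
- The next grade up reads "2 = Moderate (3 to 4 glands are plugged".
- The top grade, with nothing in between, reads "3 = Severe (All glands are plugged".

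The item is analysed. SAP section 8.11.4.6 opens its list with it ("The scores of slit lamp examination (Eyelid - Meibomian glands"). It has each score and its change listed and summarised, and it compares the Day 1 to Day 15 change between treatments with a Wilcoxon rank sum test. Protocol section 7.1.5 says the slit-lamp gradings are processed separately, so this score is not absorbed into a composite. Protocol section 7.8 and SAP section 8.5 rule out imputation.

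Protocol sections 1.1, 6.1.3 and 6.1.4.1 and SAP section 5.1 name the structures to examine but add no grading rule.

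**The concern.** An examiner who follows the scale exactly has nowhere to put an eye with more than four but fewer than ten plugged openings. The text offers no rounding rule, no nearest-grade rule and no code for an ungradable eye, although the lens scale in the same list does have a not-applicable code. The examiner must therefore choose a grade without guidance or enter nothing.

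At stake is the meaning of one analysed sign at its more affected end. A recorded 3 might mean ten plugged openings or six, and a recorded 2 might mean three or nine. A blank at either visit removes that eye from the test of change. The information may also be lost for good. The protocol asks only that relevant slit-lamp findings go into the CRF, and section 6.5.1.1 lists the slit lamp examination among data for which the CRF may be the only source. Nothing in the documents requires the count itself to be written down.

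**Working it through.** **Inputs.** Ten openings, so the possible plugged counts are 0 to 10, which is 11 values. The four grade definitions are those quoted from Protocol section 6.4.1.1. There is no sample size or power figure to reproduce for this point.

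**Step 1: map each count to a grade.**

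| Plugged openings | Grade as written |
|---|---|
| 0 | 0 |
| 1, 2 | 1 |
| 3, 4 | 2 |
| 5, 6, 7, 8, 9 | none defined |
| 10 | 3 |

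Six counts have a grade and five do not (11 − 6 = 5).

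**Step 2: see what the gap does to the analysed change.** The change is the Day 15 grade minus the Day 1 grade, so a negative value is an improvement. Three ways of handling 5 to 9 are open to an examiner: grade it 2, grade it 3, or leave it blank.

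| Count, Day 1 to Day 15 | 5–9 graded 2 | 5–9 graded 3 | 5–9 left blank |
|---|---|---|---|
| 4 to 5 | 2 − 2 = 0 | 3 − 2 = +1 | missing |
| 10 to 9 | 2 − 3 = −1 | 3 − 3 = 0 | missing |
| 10 to 5 | 2 − 3 = −1 | 3 − 3 = 0 | missing |
| 9 to 4 | 2 − 2 = 0 | 2 − 3 = −1 | missing |
| 9 to 5 | 2 − 2 = 0 | 3 − 3 = 0 | missing |

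In the first four rows the same clinical change differs by a full grade according to the choice made. If the choice is not applied consistently, an eye with six plugged openings at both visits could score 2 − 3 = −1 or 3 − 2 = +1 with no change at all.

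**Step 3: what a blank costs.** The plan has 10 subjects per arm (Protocol section 6.3.7). One unscored study eye removes 1/10 = 10% of an arm from this test, and two remove 20%.

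**Step 4: look for the source of the mismatch.** If five openings were assessed, the same four grades would cover every count (0; 1–2; 3–4; 5). Equally, with ten openings, different grade boundaries would cover every count. The text alone does not show which part is in error.

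**The case against.** The strongest reply is that little depends on this score. It is one of 11 slit-lamp items in SAP section 8.11.4.6, within one of nine secondary endpoints. The wording of that endpoint names blepharitis and other lid and conjunctival signs but not gland plugging. SAP section 8.3 calls the investigation exploratory and disclaims any regulatory claim. The primary VAS and adverse event endpoints and the sample size are untouched. All of this stands and limits the weight of the point.

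Eligibility may also keep such eyes rare. Exclusion 4 bars ocular surface disorders other than discomfort, and Protocol section 4.4 describes subjects without other ocular conditions. Whether extensive plugging falls under that wording is arguable. No criterion caps the gland count, and among dry eye severities only DEWS level 4 is excluded. Exposure may be reduced but is not ruled out.

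The CRF is not among the documents and could contain a count field or completion guidance. That is possible, but neither the protocol nor the SAP refers to one, and the written scale would still need correcting.

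A reader might infer a bias between arms. The documents do not support that. Investigators and subjects are masked (SAP section 6.5) and there is one site, so an arbitrary choice between grades 2 and 3 should fall on the arms alike.

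A reader might also count a fall from nine to five plugged openings as a change that the gap hides. Any scale that placed 5 to 9 in a single grade would score that fall as zero too. It is an argument for analysing the count, and closing the gap alone would not reveal the change.

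**Conclusion.** The point holds as a defect in a stated rule: followed exactly, the scale gives no result for five of the 11 possible counts, and nothing elsewhere in the protocol or SAP supplies one. The consequence is forced or missing values in one tested secondary item, with shifts of one grade in the change score for the affected eyes.

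Its size in practice cannot be computed. A reader might take 5/11, or 45%, as the share of eyes affected. That would require all counts to be equally likely, and the documents give no distribution of plugged glands. The number of affected eyes runs from none to many.

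The conclusion assumes that the grade lines are read literally and that no unseen CRF instruction fills the gap. It does not depend on which of the two elements, the number of openings or the grade boundaries, was intended. The expected harm is noise and missing values. The trial's primary conclusions are not affected, but the gap is worth closing because doing so is cheap.

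**What to change.** Reconcile the number of openings assessed with the grade boundaries in Protocol section 6.4.1.1 so that every possible count maps to exactly one grade. The sponsor should decide which element to change.

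Record the raw number of plugged openings in the CRF from the first baseline visit, and derive the grade from it. Add to SAP section 8.11.4.6 that the change in count is summarised and tested alongside the change in grade. The timing matters because a count has to be taken at the examination and cannot be recovered from a stored grade.

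SAP sections 4.3, 6.3 and 6.4 describe sampling, randomization and allocation in the past tense, so visits may already have taken place. In that case a new count field helps only later visits. For the earlier ones, fix a written mapping rule before unblinding, including how a grade entered without a count is treated, and list the eyes whose count is unknown.

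The cost is one CRF field and one line in the scale, with a matching sentence in the SAP. No procedure is added, since the examiner already inspects these openings.

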6.4.1.3. General procedure

Women of childbearing potential are not excluded from the study as long as adequate birth control methods are being utilized. Women of childbearing potential are defined as all women physiologically capable of becoming pregnant. Adequate birth control methods are summarized in the protocol's exclusion criteria.

Prior to enrolment in the clinical trial, female subjects of childbearing potential and their partners must be advised of the importance of avoiding pregnancy during the entire course of the study treatment and for the 30 days after the study treatment period ends and of the potential risks associated with an unintentional pregnancy. During the trial, female subjects are to be instructed to contact the Investigator immediately if they suspect they might be pregnant; in the same way, male subjects who become aware that the partner might be pregnant, are to be instructed to contact the Investigator immediately. The study Sponsor must be contacted immediately and a decision will be made regarding continuation of the pregnant woman in the study based upon the circumstances surrounding the pregnancy. Pregnancy is not reportable as an adverse event; however, complications may be reportable and will be decided on a case by case basis. A form

prepared by the Sponsor will be utilized to capture all pregnancy-related information until the birth of the child for both the subject and the partner during the study treatment period (2 weeks) and follow-up period (total 3 weeks).

Data collection – CRFs

The investigator must ensure that the clinical data required by the study protocol are carefully reported in the CRFs. He must also check that the data reported in the CRFs correspond to those in the subjects' source documents.

To ensure legibility, the CRFs should be filled out in English, in block capitals with a ball-point pen (not pencil, felt tip or fountain pen). Any correction to the CRFs' entries must be carried out by the investigator or a designated member of staff. Incorrect entries must not be covered with correcting fluid, or obliterated, or made illegible in any way. A single stroke must be drawn through the original entry. Corrections have to be dated and initialed. In the interest of completeness of data acquisition, the questions which are repeated in each section of the CRFs should be answered in full, even if there are no changes from a previous examination.

The investigator must provide a reasonable explanation for all missing data.

The CRFs will be completed, signed by the investigator, sent to the CRO Biometry Unit for data management procedures and finally sent to the Sponsor.

Unique subject identifier

All the subjects who sign the informed consent form for the present study will be coded with "unique subject identifiers" when data are extracted from the study database into the domains of the CDISC SDTM model. The unique subject identifier for study site consists of the Sponsor study code (i.e. LUB0116MD), the 3-digit screening number (e.g S01, S02, etc.) and, if applicable, the 2-digit subject study number (e.g. 01, 02, etc.).

Study code, screening number and subject study number are separated by slashes (e.g. "LUB0116MD/S01/01"). The last 5 digits of the unique subject identifier (randomized subjects), corresponding to the subject screening and subject study numbers separated by a slash, or the last 3 digits of the unique subject identifier (not randomized subjects), corresponding to the subject screening number, will appear as subject identifier in the individual listings and figures of the clinical study report and will be used to identify the subjects in in-text tables or wording (if applicable).

Coding dictionaries

Medical/surgical history and underlying diseases, physical examination abnormalities and AEs will be coded using the Medical Dictionary for Regulatory Activities (MedDRA™).

Prior and concomitant medications will be coded using the WHO Drug Dictionary Enhanced (WHODDE). Version of coding dictionaries will be stated in the study report.

Concomitant Treatments

All concomitant therapies taken during the study from screening visit to the follow-up visit must be recorded in the specific section of the CRF.

Allowed/Disallowed treatments

Use of topical cyclosporine, topical corticosteroids or any other topical medication for the treatment of dry eye in either eye is not allowed during the treatment period.

During the study follow-up period (from day 15±2 to day 22±2), any ocular topical treatments allowed, including other artificial tears/lubricants as prescribed by the treating physician.

Hormonal contraceptives for females will be allowed.

6.4.2. CRO Activities

CRO shall prepare all the documents on the need for the CI which shall be approved by Sponsor/Investigator. CRO shall follow and monitoring the entire conduction of the CI up to its conclusion. CRO shall prepare all the documents to implement the Technical File of ID (e.g. Clinical Investigational Report).

6.4.2.1. Database management

Data management of all data captured within the CRF will be performed by the CRO with the Clinical Data Management System (CDMS) according to a double data entry with total re-entry of data and discrepancy resolution by a third individual. CRO will update and verify the database and create the final SAS data sets. The tabulation datasets and analysis datasets created according to the standard CDISC (STDM and ADaM) will be provided to the Sponsor with all the other study documentation.

6.4.3. Foreseeable Bias

In order to minimize the bias the clinical study is design as randomized (1:1:1), controlled, double-masked. Subjects will enter in a 2 week double-masked, randomized, controlled treatment period. The double-masked technique is used to assure the double blind of the study.

6.4.4. Material supplied to the clinical centre

Besides the ID products, the following study material will be supplied to the clinical centre:

- CIP
- CRF for each subject plus some spare copies
- VAS forms and SANDE Questionnaires for each subjects
- copy of the investigator's brochure (IB) relative to the ID
- informed consent forms
- Urine Pregnancy Test

Moreover, before the start of the study, the investigator(s) will be provided with the following main documents: ICH guidelines, confidentiality agreement (if applicable), CIP amendments (if any), declaration of Helsinki, insurance statement, SAE forms, financial agreement (if applicable), confidential subject identification code list form, drug accountability forms, investigator and study staff list form other documents will be provided by CRO.

6.5. Monitoring, Data and Quality Management

6.5.1. Monitoring

Quality assurance is under Dompé farmaceutici s.p.a.'s responsibility.

Monitoring activities and responsibilities will be described in detail in a monitoring plan

Monitoring of the present clinical trial is assigned to CRO that has the responsibility to adequately qualify the monitoring staff and assures that the conduct of the Clinical investigation complies with the approved CIP, subsequent amendment(s), ISO 14155-2012 and the GCP.

According to the ISO 14155-2012 and the GCP, a number of measures and procedures aimed to guarantee data quality and reliability are to be applied and followed in carrying out this clinical Investigation.

6.5.1.1. Clinical monitoring and identification of source data

The study will be monitored by regular monitoring visits in compliance with ISO 14155-2012, GCP and CRO Standard Operating Procedures (SOPs) to verify data entered and collected on the CRF(s). Monitoring will be performed by the CRO.

The Investigator should agree to receive periodic monitoring visits, based on subjects' enrolment rate or for other reasons, such as to verify SAEs.

At each visit, the Investigator or a designated member of the study personnel should be available to provide direct access to all study-related documentation, including the original subject notes, and to make any necessary corrections to the CRF and/or other study documents. Source documents should be available to support the data recorded in the CRF, apart from those data for which the CRF might be accepted as being the sole source document and that will be identified prior to study commencement (physical examination, vital signs biometric measures, pregnancy test, external ocular examination, slit lamp examination, TFBUT, corneal fluorescein surface staining, Schirmer's tests I, intraocular pressure). The confidentiality of the subjects' identities shall be well protected consistent with local and national regulations when the source documents are subject to direct access.

The monitor will provide the Investigator with all the study materials before the study starts and, during the course of the study, will check at least the following:

- Full compliance with ISO 14155-2012, ICH-GCP, the study protocol and applicable regulatory requirements.
- Subject recruitment.
- Subject compliance.
- Drug accountability.
- Completeness and accuracy of the CRF data and their consistency with the source documents (appropriate source data verification will be conducted on all CRFs).
- Verification of the facilities.
- Investigator's Trial Master File.

The monitor will ensure completeness of CRFs on an ongoing basis.

Source Documents

Source data is all information, original records of clinical findings, observations, or other activities in a CI necessary for the reconstruction and evaluation of the trial. Source data are contained in source documents. Examples of these original documents, and data records include: hospital records, clinical and office charts, laboratory notes, memoranda, subjects' diaries or evaluation checklists, pharmacy dispensing records, recorded data from automated instruments, copies or transcriptions certified after verification as being accurate and complete, microfiches, photographic negatives, microfilm or magnetic media, x-rays, subject files, and records kept at the pharmacy, at the laboratories, and at medico-technical departments involved in the clinical trial.

6.5.2. Audit

The Investigator/Institution must allow Dompé farmaceutici s.p.a. and/or independent bodies acting on behalf of the Sponsor and CRO to have the right to perform the audits as an integral part of the quality assurance system.. The audit is an independent verification, separate from the monitoring activity, of the activities and of the documents to ensure that the activities pertinent to

the study were duly carried out and that they were recorded, analyzed and transferred in compliance with the protocol, ISO 14155, GCP, relevant SOPs and with applicable legislation.

6.5.3. Inspections

The Investigator/Institution must allow national and foreign Regulatory Authorities to conduct inspections.

The Inspection on the part of one or more Regulatory Authorities consists of an official review of the documents, facilities, records and any other resource considered by the authorities to be connected with the study.

7. STATISTICS

7.1 Design, Methods and Analytical Procedures

7.1.1 Statistical Methods

The data documented in this study will be listed by subject, treatment, eye (enrolled eye(s), left and right) and evaluation time point, i.e Baseline or Day 1 (Visit 1), Day 15 ±2 (Visit 2) and follow-up (Visit 3).

Appropriate descriptive statistics will be used according to the nature of the variable.

Not available data will be evaluated as “missing values”. The statistical analysis will be performed using SAS® version 9.3 (TS1M1) for Windows® (19) or higher.

7.1.2 Definitions

A subject will be defined as screened after the signature of the informed consent, regardless of the completion of all the screening procedures.

A subject will be defined as randomized in the study if he/she is assigned to a treatment arm (Test 1 (20 µg/mL), Test 2 (50 µg/mL) or Control).

- Enrolled set: all enrolled subjects. This analysis set will be used for demographic, baseline and background characteristics
- Full Analysis Set (FAS): all randomized subjects, who receive at least one dose of the ID. This analysis set will be used for the efficacy analysis
- Safety set: all subjects who receive at least one dose of the investigational medicinal product(s). This analysis set will be used for tolerability and safety analyses

Each subject will be coded by the CRO Biometry Unit as valid or not valid for the Enrolled set, FAS and Safety set. Subjects will be evaluated according to the treatment dose they will actually receive.

7.1.3 Demographic, Baseline and Background Characteristics

Standard continuous or categorical variable summaries will be used for demographic and population characteristics. Data will be presented for Baseline visit.

7.1.4 Tolerability and Safety Evaluation

AEs

Adverse events (AEs) will be coded by System Organ Class (SOC) and Preferred Term (PT), using the Medical Dictionary for Regulatory Activities (MedDRA).

AEs will be classified as pre-treatment AEs (PTAEs) and treatment-emergent AEs (TEAEs), according to the period of occurrence, as follows:

- PTAEs: all AEs occurring before the first dose of the ID and not worsening after the first dose of the IMD
- TEAEs: all AEs occurring or worsening after the first dose of the ID

Individual PTAEs and TEAEs will be listed in subject data listings. No summary table will be provided for PTAEs. TEAEs will be summarized by dose and overall. The number and percentage of subjects with any TEAE and the number of TEAEs will be tabulated by SOC and PT, seriousness, relationship to treatment and severity.

A summary of adverse events leading to premature withdrawal will be provided, grouped by body system and preferred term.

Visual analogue scale (VAS)

Local ocular tolerability score will be performed before any ophthalmic assessment at a given study visit. Specific ocular symptoms to be assessed with the VAS include: dryness, foreign body sensation; burning/stinging; itching; pain; sticky feeling; blurred vision; photophobia. Time profile of treatments will be analyzed according to analysis of variance for repeated measure model.

